- 7 In case of dose decrease, an unscheduled visit should be planned within the week following the phone contact in order to decrease the dose from 20 to 10 mg. The other doses decrease, from 40 to 20 and 10 to 5 mg, don't require a visit.

ABBREVATIONS USED IN THE PROTOCOL

AEs Adverse events

ALAT Alanine aminotransferase

ANCOVA Analysis of Covariance test

ASAT Aspartate aminotransferase

AUC Area under the concentration-time curve

BMI Body mass index

CASS Child and Adolescent Sleepiness Scale

CDI Childhood Depression Inventory

CGI-C Clinical Global Impression of Change

CGI-S Clinical Global Impression of Severity

Cmax Maximum observed concentration

CNIL Commission Nationale de l'Informatique et des Libertés

CNS Central nervous system

CRF Case report form

CRO Contract Research Organization

CSF Cerebral Spinal Fluid
CSR Clinical Study Report

C-SSRS Columbia-Suicide Severity Rating Scale

DMB Data Management Book

DSM-IV Diagnostic System Medical, fourth version

DSMB Data Safety Monitoring Board

ECG Electrocardiogram

EDS Excessive Daytime Sleepiness

FAS Full Analysis Set

GCP Good Clinical Practice

GGT Gamma glutamyltransferase
GMP Good Manufacturing Practice

H3R Histamine H3 receptor

ICH International conference on harmonization of technical

requirements for registration of pharmaceuticals for human use

ICSD International Classification of Sleep Disorders

IEC Independent Ethics Committee

IRB Institutional Review Board

BIOPROJET Version 3.0
Protocol P11-06/ BF2.649 September 30th, 2020
EudraCT number: 2013-001506-29

KO Knock-out

MSLT Multiple Sleep Latency Test

MWT Maintenance of Wakefulness Test
NOAEL No observable adverse effect levels
OSA Obstructive Sleep Apnoea syndrome

PDSS Pediatric Daytime Sleepiness Scale

PS Paradoxical sleep
PSG Polysomnography

REM Rapid Eye Movement
SAE Serious Adverse Event

SD Standard Deviation

TEA-Ch Test of Everyday Attention for Children

ß-hCG Human chorionic gonadotropin

SWS Slow Wave Sleep
Tmax Time to Cmax

1. INTRODUCTION

Narcolepsy is a sleep disorder characterized by excessive daytime sleepiness (EDS). The ageat-onset may be childhood, and even more disabling symptoms such as cataplexy attacks can very often occur (80 % of cases approximately, according to renowned European neurologists). Cataplexy attacks facilitate the Δg since, in young children, sleepiness may take on the form of an increased rather than a decreased activity, including irritability, aggressiveness, and inattentiveness (resembling the attention-deficit/hyperactivity disorder).

Pharmacological treatments consist of psychostimulants (modafinil, methylphenidate), whereas sodium oxybate is used to reduce the frequency and intensity of cataplexy attacks.

However, a great number of adverse events (more particularly, confusion, dizziness, suicidal ideation, high blood pressure...) together with its administration rhythm requiring a nocturnal intake (not easily followed by patients) restrict its use.

Pitolisant, an inverse agonist of H3 receptor, has been developed in adult, narcoleptic patients with or without cataplexy, during several phase II (P04-03, P05-03, P06-06) and phase III (P07-03, P07-07, P09-15) clinical studies, with a good tolerance followed by favorable efficacy results, since it significantly reduced the diurnal sleepiness, as well as the number of cataplexy attacks.

Version 3.0 Protocol P11-06/ BF2.649 EudraCT number: 2013-001506-29 September 30th, 2020

[figure not shown]
SUMMARY OF RELEVANT NONCLINICAL STUDIES

Pharmacological Profile *1.1.1.*

1.1.

I		

[figure not shown]
1.2. SUMMARY OF RELEVANT CLINICAL STUDIES

1.2.1. Phase I studies

1.2.1.1. Phase I studies in adults

[figure not shown]

[figure not shown]

[figure not shown]

[figure not shown]

			j	
e e				
·	· !		і	
	· !	Ė		
	' =			
	 			
	•	Ė	┇	

[figure not shown]

[figure not shown]

[figure not shown]

[figure not shown]

[figure not shown]

[figure not shown]

1.3. SUMMARY OF THE KNOWN AND POTENTIAL RISKS AND BENEFITS TO HUMAN SUBJECTS

The exposure to pitolisant in healthy volunteers was assessed in six pharmacokinetic studies in 66 subjects that received doses of pitolisant in single administration up to 120 mg and during 28 days with 50 mg once daily. The compound was well tolerated up to 90 mg by single dose; however the single dose at 120 mg led to irritability. The repeated administration (28 days up to 50 mg/day) was well tolerated.

Phase II studies demonstrated the positive effect of pitolisant in Excessive Daytime Sleepiness reduction in the indications intended for clinical trials.

The tolerance was good and the most common adverse events with pitolisant were headache (9.5%), insomnia (9.3%) and middle insomnia (0.9%), nausea (4.3%) and irritability (3.2%). These adverse events were most of the time of mild to moderate intensity.

[figure not shown]
Both phase III pivotal studies performed in 94 and 165 narcoleptic patients with or without cataplexy, respectively, all of them being treated by pitolisant, modafinil, or placebo during 8 weeks and analyzed, confirmed the efficacy of pitolisant on excessive daytime sleepiness with effects statistically superior to those of the placebo at the level of the main efficacy endpoint (ESS score), but also at the level of secondary criteria such as MWT, SART, CGI (on EDS), and above all the "ESS responder" criterion (ESS \leq 10, or ESS Final – ESS Baseline \geq 3).

The analysis of sleep diaries completed by the patients during 7 days prior to each visit showed a possible reduction of the risks of cataplexy, which remains to be confirmed by a new clinical study in this indication.

Tolerance was checked in more than 50 patients treated during 12 months by pitolisant only, or in association with other products (P09-10). It was found to be excellent in both groups.

2. RATIONALE FOR THE STUDY

 ·	·	

Version 3.0

3. TRIAL DESCRIPTION

TRIAL OBJECTIVES

BIOPROJET

During this trial, pitolisant will be compared to placebo, with regard to EDS on the one hand, and to the number of cataplexy episodes, if any, on the other hand.

The clinical and biological tolerance of pitolisant will also be checked.

This trial will characterize the efficacy of pitolisant (5-, 10-, 20-, 40 mg/d in Double Blind Period and 5-, 10-, 15-, 20-, 30-, 40 mg/d in Open Label Period) compared to placebo in showing an incremental improvement to the situation particularly in terms of a reduction of EDS as measured by the UNS, and also on the number of cataplexy episodes, if any.

3.2. TRIAL DESIGN

Randomized, double blind, placebo-controlled, parallel group, multicentre trial comparing the effects of pitolisant or placebo for the treatment during 8 weeks (double-blind period) of narcoleptic patients with or without cataplexy. After 4-week of individual up-titration scheme from 5 to a maximum of 40 mg/d pitolisant or placebo, the treatment will be administered at a stable dose during 4 weeks, followed by 1 week placebo period.

Then, patients willing to continue will receive the study treatment during a prolonged openlabel period. BIOPROJET Protocol P11-06/ BF2.649 EudraCT number: 2013-001506-29

3.3. STUDY ENDPOINTS

3.3.1. Primary Endpoint

The primary endpoint of efficacy will be the changes in UNS (Ullanlinna Narcolepsy Scale) measuring the intensity and frequency of symptoms of narcolepsy (Excessive Daytime Sleepiness (EDS) and cataplexies), based on the change from baseline (mean of two pretreatment measures at [(V1 + V2)/2]) of the UNS score and at the end of double-blind phase (mean of the last two measures [(V6 + V7)/2]).

3.3.2. Secondary endpoints

As secondary endpoints the study will assess efficacy and safety endpoints in pitolisant and placebo groups:

- Changes in EDS as measured by the maintenance of wakefulness test (MWT) between baseline and V7,
- Changes in EDS measured by the Paediatric Daytime Sleepiness Scale (PDSS) between baseline: [V1 score (D-14) + V2 score (D0)]/2 and the end of treatment: [V6 score (D49) + V7 score (D56)]/2,
- Changes in EDS as measured by the Child and Adolescent Sleepiness Scale (CASS) between baseline and the end of treatment.
- Changes in the average number of cataplexy episodes per weeks: (recorded in sleep diary by patient and/or parent/teacher) between the 2 weeks of baseline and the 2 weeks of end study treatment period (V6, V7),
- Differences in weekly frequency of cataplexy episodes (recorded in sleep diary by patient and/or parent/teacher) between baseline and the 4 weeks of stable treatment period (V4 to V7),
- Severity of EDS measured by the clinical Global Impression of severity and change. Changes between baseline and V6, V7,
- Severity of cataplexy measured by the clinical Global Impression of severity and change. Changes between baseline and V6, V7,
- Changes between baseline and V6 will be compared for the TEA-Ch test,
- Comparison between placebo and pitolisant groups on:
 - Withdrawal symptoms questionnaire (DSM IV) on D59 during a phone call (T1) and at the end-of-study visit on D63 (V8) after a one-week period on placebo,
 - Patients' Global Opinion on treatment effect at the end of treatment if able to express

Protocol P11-06/ BF2.649 EudraCT number: 2013-001506-29

himself. If not will be reported either by parents or teachers.

- ,Tolerability as measured by Treatment Emergent Adverse Events (TEAE),
- Changes in Physical examination and Vital signs,
- ECG and calculation of Fridericia's corrected QTc interval (QTcF = $QT/\sqrt{3}\sqrt{60/HR}$),
- Blood laboratory tests (haematology, blood chemistry),
- Mood appraisal adapted to children (CDI and C-SSRS).
- Changes between baseline and at each visit of the open-label period in EDS,
- Safety assessment will be done on monitoring of adverse events, physical examination, vital signs, ECG and Blood Laboratory tests modifications and the mood appraisal throughout the study.

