- 13) Active clinically significant illness, including unstable cardiovascular, endocrine, neoplastic, gastrointestinal, haematological, hepatic, immunologic, metabolic, neurological (other than narcolepsy/cataplexy), pulmonary, and/or renal disease which could interfere with the study conduct or counter-indicate the study treatments or place the patient at risk during the trial or compromise the study objectives.
- 14) Prior severe adverse reactions to CNS stimulants.
- 15) Known hypersensitivity to the tested treatment including active substance and excipients.
- 16) The inability to continue daily activities safely, without the use of treatment against EDS.
- 17) Any patient presenting congenital galactosemia, glucose-galactose malabsorption or lactase deficiency due to the presence of lactose in investigational treatments.
- 18) Patients participating in another study or being in a follow-up period for another study.
- 19) Cannot be contacted in case of emergency.

STUDY TREATMENT

Patients will be outpatients followed in ambulatory way during the whole study period and they will all receive the investigational study treatment pitolisant or placebo as described § 4.2. Patients will be asked to take the study drug every day before breakfast, according to the investigator's prescription regarding the dose regimen of patients, based on the product efficacy

and tolerance.

The total treatment duration of this double blind study is 8 weeks. Patients will start pitolisant treatment with escalating doses scheme on the first 4 weeks, as follows:

- V2 5 mg of BF2.649 or placebo / day during the first week,
 - 10 mg of BF2.649 or placebo /day during the second week,
- V3 Increase to 20 mg/d or maintain at 10 mg/d or reduce to 5 mg/d of BF2.649 (or placebo) per day for 7 days depending on efficacy and tolerability.

- V4 It will also be possible to reduce the dose administered to the patients, or to increase it without exceeding 40 mg/d. Patients with a weight less than 40kg could be treated with a maximum daily dose of 20mg.
- V5 It will be possible to reduce the dose administered to the patients, but not to increase it.
 - As from V5 onwards, no dosage change of the study treatment will be authorized.
- At the end of the double blind treatment (V7), the investigator will provide placebo to all patients for the one-week wash out period.

In open-label period patients will start pitolisant treatment with escalating doses scheme, as follows:

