3.7.1.2.6. Patient sleep diary

Patient sleep diary (Appendix 6) information from V1 (or from V0 when applicable) to V8 will be analyzed.

Patients (or assisted by their parents or legal representative or teacher) shall fill in the document on a daily basis throughout the double blind phase (13 weeks) and the 7-day prior to the next visit during the open-label period. During the first screening visit (V1 or from V0 when applicable), patients will be instructed on the daily use of diary by study investigators.

At each visit the patient should bring back his/her diary to the site for review by the investigator. The investigator should review these records with the patient.

In the active treatment group and in the placebo group, the score difference between the average number of cataplexy episodes (partial and total) per weeks between the 2 weeks of baseline and the 2 weeks of end study treatment period (V6, V7) and the differences in weekly frequency of cataplexy episodes between baseline and the 4 weeks of stable treatment period (V4 to V7).

In the open-label period, the difference between, the average number of cataplexy episodes

(partial and total) per weeks, the differences in weekly frequency of cataplexy episodes, between baseline and the 7-day prior all visits of the open-label period will be compared.

From the sleep diary, it will also be possible to check: Investigator should review the patients' and parents' estimate with them

- Hour of bedtime in the evening, wake-time in the morning.
- Number of diurnal involuntary sleep attacks and episodes of severe daytime sleepiness.
- Occurrence and number of cataplexy attacks (total or partial).
- Number of hallucinations and sleep paralysis.

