BF2.649 at 5 mg/day: 1 tablet of BF2.649 5 mg or placebo in the morning during 7 days, or BF2.649 at 10 mg/day: 2 tablets of BF2.649 5 mg or placebo in the morning during 7 days, or BF2.649 at 20 mg/day: 1 tablet of BF2.649 20 mg or placebo in the morning during 7 days, or BF2.649 at 40 mg/day: 2 tablets of BF2.649 20 mg or placebo in the morning during 7 days. Treatment dosage at 40mg/day not allowed for patient with a weight less than 40 kg.

- -V5 (D28±2): No increase of BF2.649 dosage will be authorized, but it will be possible to decrease the dose, if the tolerance requires it. From this visit onwards, no dose change will be allowed.
- Week 5 to week 8: according to the investigator's prescription patients for whom the optimal dose level is estimated will continue at the same dose or the level dose will be reduced based on the tolerance to the product.

BF2.649 at 5 mg/day: 1 tablet of BF2.649 5 mg or placebo in the morning during 28 days, or BF2.649 at 10 mg/day: 2 tablets of BF2.649 5 mg or placebo in the morning during 28 days, or BF2.649 at 20 mg/day: 1 tablet of BF2.649 20 mg or placebo in the morning during 28 days, or BF2.649 at 40 mg/day: 2 tablets of BF2.649 20 mg or placebo in the morning during 28 days. Treatment dosage at 40mg/day not allowed for patient with a weight less than 40kg.

- V7 (D56± 2): Prescription of 1-week of placebo for all patients.

In open-label period patients will start pitolisant treatment with escalating doses scheme, as follows:

- V8 (D63 \pm 2)
- Week 10: BF2.649 at 5 mg/day: 1 tablet of BF2.649 5 mg in the morning during 7 days.
- Week 11: BF2.649 at 10 mg/day: 2 tablets of BF2.649 5 mg in the morning during 7 days.
 - $-V9 (D77\pm 2)$:
- Week 12: according to the investigator's prescription patients for whom the optimal dose level is estimated will continue at the same dose or if not sufficiently improved in their symptoms, and with a good tolerance, will increase to a higher dose or the level dose will be reduced based on the tolerance to the product.

BF2.649 at 5 mg/day: 1 tablet of BF2.649 5 mg in the morning during 7 days, or

EudraCT number: 2013-001506-29

BF2.649 at 10 mg/day: 2 tablets of BF2.649 5 mg in the morning during 7 days, or BF2.649 at 20 mg/day: 1 tablet of BF2.649 20 mg in the morning during 7 days, or

 $-V10 (D84\pm 2)$:

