5. CONDUCT OF THE STUDY

5.1. **EXPECTED DURATION OF SUBJECT PARTICIPATION**

The expected duration of patient participation from the screening visit (V0) until the final visit

Confidential 71

BIOPROJET Version 3.0 Protocol P11-06/ BF2.649 September 30th, 2020

EudraCT number: 2013-001506-29 (V8) will be 13 weeks:

Baseline period without investigational treatments (from V0 to V2): 4 weeks.

• Low and medium dose titration phase (from V2 to V3): 2 weeks

• Individual dose adjustments (from V3 to V5): 2 weeks

• Stable dose phase (from V5 to V7): 4 weeks

• 1-week study drug wash out (placebo) after study drug discontinuation

During the double blind phase, the patient will be followed in an ambulatory way by 9 visits on the site.

The double blind phase will be followed by a prolonged open-label period if patient wishes, until BF2.649 (pitolisant) is available on the marketfor children/adolescent from 6 to 17 years included or as soon as the patient becomes older than 18 years. Then, he will have access to the treatment already on the market for adults.

The first inclusion of this study is scheduled in Q1 2016. The end of the double-blind phase is expected by Q1 2022.

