5.2.5. V4 – Dose adjustment visit (Day 21 ± 2 days)

A complete interrogation including occurred of possible adverse events and concomitant

medication used will be done and recorded,

A physical examination including vital signs shall be carried out,

12-lead ECG recording with calculation and control of QTcF,

The following questionnaires should be performed:

- PDSS,

- CASS,

- CDI,

- C-SSRS,

- Retrieval of sleep diary of the previous visit and check by the investigator. Delivery of one

other sleep diary which have to be completed every evening until the next visit.

Investigational treatment allocation: the dose of pitolisant will be individually adjusted

according to the investigator's prescription patients for whom the optimal dose level is

estimated will continue at the same dose or if not sufficiently improved in their symptoms, and

EudraCT number: 2013-001506-29

with a good tolerance, will increase to a higher dose or the level dose will be reduced based on

the tolerance to the product. Dose allocation: either 5, 10, 20 or 40 mg/day or placebo in the

morning during 7 days. Patients with a weight less than 40kg could be treated with a maximum

daily dose up to 20 mg.

The treatment pack bring back from previous visit by patient is checked by investigator for the

compliance. Investigator will remind patient to bring back the investigational treatment packs

at the next visit.

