# $\circ$ Treatment Emergent Adverse Events in the stable dose period

The stable dose is the treatment dose taken during the period V5 to V7. So TEAE in the stable dose are TEAE occurred between visit V5 (included) and the visit V7 (included)

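### The cataplexy diary windows do not match their stated lengths: V4 to V7 is five weeks and includes a dose-adjustment week, and V6 to V7 is either one week or two weeks that include the placebo wash-out.

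*Protocol*

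**What the plan says.** **Stable-dose window in the endpoints.** Protocol 3.3.2 compares weekly cataplexy frequency "between baseline and the 4 weeks of stable treatment period (V4 to V7"). The synopsis has the same definition, and the sleep diary section (3.7.1.2.6) repeats "the 4 weeks of stable treatment period (V4 to V7").

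**Stable-dose phase elsewhere.** Protocol 5.1 lists individual dose adjustment from V3 to V5 and then "Stable dose phase (from V5 to V7): 4 weeks". The synopsis entry for V5 starts the four stable weeks at that visit, and SAP 3.3.1 has the same timeline. For adverse events, SAP 4.1.5.6 states: "The stable dose is the treatment dose taken during the period V5 to V7".

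**Dosing around V4 and V5.** Protocol 5.2.5 is headed "V4 – Dose adjustment visit (Day 21 ± 2 days"). The study treatment section allows the dose at V4 to be reduced "or to increase it without exceeding 40 mg/d". Section 4.2 then says "V5 (D28±2): No increase of BF2.649 dosage will be authorized". A reduction is still possible at V5, and no change is allowed after it.

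**End-of-treatment window.** Protocol 3.3.2 and 3.7.1.2.6 also define a change in weekly episodes over the final two weeks of treatment, identified by V6 and V7.

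**SAP.** Section 4.5.3.2.3 tests WRC over V6 to V7. For descriptive statistics it gives D21 to D63, labelled both six weeks and V4 to V7, and D49 to D63, labelled both two weeks and V6 to V7. Section 4.5.3.3.6 uses the same day ranges for the other diary variables. Section 4.1.5.5 counts the days in a period as last visit date minus first visit date plus one. Section 4.6 lists no modification from the protocol.

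**The concern.** In each window the stated length, the visit labels and, in the SAP, the day numbers cannot all be right. A programmer who follows the visit labels, as the SAP's day count directs, gets one set of diary days. One who follows the stated weeks or the SAP's day ranges gets another.

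For the four-week endpoint, the label brings in a week that the protocol itself classes as dose adjustment, under a name that promises stable treatment. For the two-week endpoint, the choice lies between half the stated time and a period that includes a week on placebo for everyone. That second ambiguity matters more, because WRC is fourth in the fixed testing sequence (SAP 4.1.3.2). If the window is settled only after unblinding, the choice can be challenged as data-driven.

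**Working it through.** **Inputs (nominal days, Protocol 4.2, section 5.2 and the visit schedule).** V4 = D21, V5 = D28, V6 = D49, V7 = D56, V8 = D63, each ±2 days. All patients take placebo from V7 to V8.

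**Step 1: the stated four weeks.** Length = day of last visit minus day of first visit.

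| Window | Calculation | Days | Weeks | Range with ±2-day windows |
|---|---|---|---|---|
| V4 to V7 | 56 − 21 | 35 | 5 | 31 to 39 days |
| V5 to V7 | 56 − 28 | 28 | 4 | 24 to 32 days |
| V6 to V7 | 56 − 49 | 7 | 1 | 3 to 11 days |
| V4 to D63 | 63 − 21 | 42 | 6 | 38 to 46 days |
| V6 to D63 | 63 − 49 | 14 | 2 | 10 to 18 days |

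The four weeks are reproduced by V5 to V7 and not by V4 to V7. Even at the extremes of the visit windows V4 to V7 is at least 31 days, so it cannot be 28. The SAP's inclusive count makes it 36.

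**Step 2: what the extra week is.** D21 to D28 is V4 to V5, the second week of the V3 to V5 adjustment phase. Its share of V4 to V7 is 7/35 = 20%. Across the visit windows the share runs from 3/35 = 8.6% to 11/35 = 31.4%.

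**Step 3: the SAP's D21 to D63.** Of the 42 days, 7 are adjustment (7/42 = 16.7%), 28 are stable dose (28/42 = 66.7%) and 7 are placebo wash-out (7/42 = 16.7%). The SAP labels this V4 to V7, but D63 is V8.

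**Step 4: the stated two weeks.** By visit dates V6 to V7 is 7 days, or 8 by the SAP's inclusive count. The SAP's D49 to D63 is 14 days, of which 7 (50%) are placebo wash-out. Neither reading gives two weeks on study treatment at a stable dose.

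**Step 5: a window that does.** The 14 days up to V7 are about D42 to D56. At the earliest V7 (D54) they start at D40, and the latest V5 is D30, so within the visit windows they lie wholly in the stable-dose phase. The schedule of events requires the diary every evening up to V8, so these days are already recorded.

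**The case against.** The strongest reply is that this is a labelling slip with little consequence. Much of that stands.

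- **Dosing.** A reader might infer that doses are still being raised during D21 to D28. They are not. The last permitted increase is made at the V4 visit, and that dose is then taken for the week. A patient who is not reduced at V5 takes the final dose throughout V4 to V7. What remains is that the week is an adjustment week by the protocol's own timeline, and its dose may still be cut at V5.
- **Dilution.** A reader might infer that the stable-dose effect is understated by up to a fifth. That holds only if the week shows no effect at all. If it showed 0%, 50% or 100% of the stable-dose effect, the V4 to V7 average would show (28 + 7 × 0)/35 = 80%, (28 + 7 × 0.5)/35 = 90%, or 100% of it. These are assumptions. Patients have had three weeks of study treatment by V4, and those reduced at V5 took a higher dose in that week than afterwards, so the direction could reverse.
- **Inference.** No planned test uses V4 to V7; in the SAP it is descriptive.
- **Diary time.** A reader might infer that the WRC test simply discards half of the intended diary time. That is one of two readings, because the SAP's own gloss on V6 to V7 is 14 days, ending at D63. Nor can a gain in precision from 14 evenings be quoted: the documents give no episode rate or dispersion, and the planned comparison is a baseline-adjusted negative binomial model.

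The reply does not remove the contradiction, and it does not settle which days enter the WRC test.

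**Conclusion.** The concern holds as a contradiction between stated lengths, visit labels and day ranges. V4 to V7 is five weeks, one of which (20%) is dose adjustment. The SAP's version is six weeks, one sixth adjustment and one sixth placebo wash-out. V6 to V7 is one week by visit dates, or two weeks of which half is placebo wash-out.

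These figures rest only on nominal visit days. The first fault affects a named protocol secondary endpoint that is descriptive in the SAP. The second leaves the data window of a test in the fixed sequence undefined, and is the more important. The effect on the estimates is unknown in size and direction. The correction should be made, but nothing here touches the primary UNS analysis.

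**What to change.** - **Stable-dose window.** In the protocol synopsis, 3.3.2 and 3.7.1.2.6, and in SAP 4.5.3.2.3 and 4.5.3.3.6, define it as V5 to V7 (D28 to D56).
- **Two-week window and WRC test.** In the same places, define both as the last 14 diary days up to V7 (about D42 to D56), ending at V7 and not at D63. Other reconciliations are possible, but this one delivers the stated two weeks wholly on stable dose.
- **Day count.** Align the rule in SAP 4.1.5.5, since visit dates no longer delimit the 14-day window.
- **Record.** Note the clarification in SAP 4.6, before unblinding.

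The cost is wording and a small programming change. No visit, dose or data collection changes, because the diary is already completed every evening.
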